7.1.3 Double-Blind Placebo-Controlled Treatment Phase (Visits 2 to 22)

The duration of the DBPC treatment phase will be 2 years (104 weeks). Trial visits during this phase are outlined in [Table 2](#), and details of the procedures to be performed are presented in [Appendix E](#).

Table 2 Trial Visits during DBPC Treatment Phase

Visit Number	Week*	Treatment	Visit Name or Type
2	0	X	Baseline – Major Efficacy
3	1	X	
4	2	X	
5	3		
6	12		Minor Efficacy
7	26	X	Major Efficacy
8	27	X	
9	28	X	
10	29		
11	38		Minor Efficacy
12	52	X	Major Efficacy
13	53	X	
14	54	X	
15	55		
16	64		Minor Efficacy
17	78	X	Major Efficacy
18	79	X	
19	80	X	
20	81		
21	90		Minor Efficacy
22	104		Major Efficacy

* Relative to randomization and initiation of therapy at Week 0. Assessments performed at “major” and “minor” efficacy visits are described in Sections 7.1.3.3 and 7.1.3.4 respectively.

Subject eligibility for the trial will be confirmed at the baseline visit (Week 0/Visit 2; see Section 7.1.3.1) based on scores for Question 1 of the WOMAC pain index at screening and baseline (see Section 5.4). Eligible subjects will then be randomized and the first i.a. injection of IMP will be administered.

I.a. injections of the IMP will be administered at the baseline visit (Week 0/Visit 2) and at the visits identified in Section 7.1.3.2.

Major efficacy assessments will take place at intervals of 6 months, at the beginning of each treatment cycle and at the end of the DBPC treatment phase (Week 104/Visit 22; see Section 7.1.3.3).

Minor efficacy assessments will also take place at intervals of 6 months, occurring 9 weeks after the end of each treatment cycle (see Section 7.1.3.4).

Subjects will be requested to discontinue the intake of all pain medications for 5 half-lives before a visit involving completion of the WOMAC (see Sections 5.4 and 7.1.2). At least 3 days before each such visit, subjects will be contacted by phone to remind them of this requirement. When

the upcoming visit includes injection of IMP, this phone contact will include a reminder to complete trial diary information about target knee pain and swelling for the day before the visit.

Vital signs measurement (see Section 7.4.4) and review of AEs and concomitant medications (see Sections 7.4.1 and 6.5) will be performed at all DBPC treatment phase visits.

For women of childbearing potential, urine pregnancy tests will be performed before dosing on each treatment day (see Section 7.1.3.3).

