7.1.3.2 IMP Administration

Subsequent IMP injections will be given at the following time points:

- Cycle 1: Weeks 1 and 2 (Visits 3 and 4)
- Cycle 2: Weeks 26, 27, and 28 (Visits 7, 8, and 9)
- Cycle 3: Weeks 52, 53, and 54 (Visits 12, 13, and 14)
- Cycle 4: Weeks 78, 79, and 80 (Visits 17, 18, and 19).

At visits where IMP is administered, all procedures should be performed before dosing unless otherwise specified. Urine pregnancy testing will be conducted in women of childbearing potential prior to each injection.

Immediately prior to dosing at each of these visits, the Investigator or delegate will obtain a blinded treatment kit number from the IVRS as described in Section 6.3. Medication from the assigned treatment kit will be prepared as described in Section 6.2 and administered i.a. according to instructions in the MOP.

- Using aseptic technique, i.a. administration will be guided by ultrasound to ensure delivery of the IMP into the joint space.
- Before injecting the IMP solution, an aspiration of the synovial fluid for PK and biomarker analysis will be performed as part of the i.a. injection procedure, using the same needle that will be used for injection. If possible, up to 2.5 mL should be collected (instructions for sample handling are provided in the MOP).

At visits where samples are collected for PK analyses (see [Appendix E](#)), subjects will be requested to stay in the study site for approximately 2 hours post-injection for collection of the

post-dose samples. At visits where biomarkers are collected, samples will be collected in the fasting state.

7.1.3.3 Major Efficacy Visits (Weeks 26, 52, 78, and 104; Visits 7, 12, 17, and 22)

Major efficacy visits will take place at intervals of 6 months (on the first day of each treatment cycle) and then at the end of the DBPC treatment phase (Week 104/Visit 22).

The following procedures will be performed at major efficacy visits. At visits where IMP is administered, all procedures should be performed before dosing unless otherwise specified. Subject questionnaires (WOMAC, PGA, KOOS QOL, KOOS Symptom Index, PGIC, NRS pain score in the target and contralateral knee, MOS SF-36, pain in other joints, and ICOAP) should be completed before any other procedures are performed; the WOMAC should be completed first.

- WOMAC (see [Appendix C](#))
- PGA (see Section [7.3.3](#))
- KOOS QOL (see [Appendix D](#))
- KOOS Symptom Index (see [Appendix D](#))
- PGIC (see Section [7.7.4](#))

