7.4.3 Laboratory Assessments

Standard laboratory assessments in this trial will consist of hematology, clinical biochemistry, and urinalysis panels: complete lists of parameters are presented in [Appendix B](#).

As an exogenous protein, sprifermin has the potential to trigger antibody formation, which could conceivably have safety, PK, or efficacy implications. Thus, subjects will be tested for binding and neutralizing antibodies to sprifermin/FGF-18. Only samples that are found to be positive for binding antibodies will be tested for neutralizing antibodies.

Blood, urine, and synovial fluid samples for laboratory assessment will be collected at the time points indicated in [Appendix E](#).

- Subjects are not required to fast before routine laboratory sample collection in this protocol, however, an 8-hour fast is required before blood or urine sample collection for biomarkers.
- For time points where IMP injections are administered, blood and urine samples will be collected pre-dose.
- For measurement of biomarkers in urine, second morning void samples should be obtained.
- Synovial fluid samples will be collected immediately before injection of the IMP as described in the MOP.

PK assessments are described in Section 7.5, and biomarker and PGt assessments are described in Section 7.6.

All laboratory assessments will be performed centrally. Instructions for sample collection, handling, and shipment are provided in the MOP.

Pregnancy Tests

For women of childbearing potential, pregnancy tests will be performed at the time points shown in [Appendix E](#) (during screening, before each injection of IMP, and at each visit involving X-ray and MRI). A serum test will be performed during screening, and urine tests will be performed at subsequent time points.

Management of Subjects with Laboratory Abnormalities

Laboratory abnormalities that Investigators consider to be clinically significant should be reported as AEs (see Section 7.4.1).

The best interest of the participating subject will always come before that of the trial. Abnormalities of any safety laboratory analysis considered to represent a significant danger to the subject will lead to immediate discontinuation of the drug, and the Medical Responsible must be informed immediately.

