Surgical procedures (target knee)	Continuous																	
Review of subject diaries	X	X	X	X	X	X	X	X	X	X	X	X	X	X	X	X	X	X
Vital signs ⁽²⁾	X	X	X	X	X	X	X	X	X	X	X	X	X	X	X	X	X	X
Physical examination ⁽³⁾	X				X	X				X	X	X	X	X	X	X	X	
ECG	X										X							
Clinical laboratory specimens ⁽⁴⁾	X					X					X	X	X	X	X	X	X	
Antibodies to sprifermin/FGF-18	X			X		X			X		X							
PK serum collection ⁽⁵⁾			X					X			X							
Biomarker serum collection ⁽⁶⁾			X					X			X							
Biomarker urine collection			X					X			X							
PGt sample collection ⁽⁷⁾	One sample is needed. It can be taken at any trial visit.																	
Pregnancy test (urine) ⁽⁸⁾	X					X					X		X		X		X	
20-meter walk test	X				X	X				X	X	X	X	X	X	X	X	
Knee X-ray ⁽⁹⁾⁽¹⁰⁾	X										X		X		X		X	
Target Knee MRI ⁽¹⁰⁾	X					X					X		X		X		X	
Synovial fluid collection ⁽¹¹⁾	X	X	X			X	X	X										
i.a. injection of IMP	X	X	X			X	X	X										

Table footnotes appear on following page.

Abbreviations: AEs: adverse events; ECG: electrocardiogram; i.a: intra-articular; ICOAP: Measure of Intermittent and Constant Osteoarthritis Pain; KOOS: Knee Injury and Osteoarthritis Outcome Score; MRI: magnetic resonance imaging; NRS: numerical rating scale; PGIC: Patient Global Impression of Change; PK: pharmacokinetic; QOL: quality of life; WOMAC: Western Ontario and McMaster Universities Osteoarthritis Index
ET: Early Termination (procedures shown for this visit should be performed at the time of early treatment discontinuation or trial withdrawal.) EF: Extended follow-up.

Subjects will be requested to discontinue the intake of any pain medications for at least 5 half-lives before a visit involving completion of the WOMAC.

At visits where IMP is administered, all procedures should be performed before dosing unless otherwise specified. Subject questionnaires (WOMAC, PGA, KOOS QOL, KOOS Symptom Index, PGIC, NRS in both knees, pain in other joints, MOS SF-36, and ICOAP) should be completed before any other procedures are performed; the WOMAC should be completed first.

At each visit, subjects will be given trial diaries which will be collected and reviewed at the following visit (see Section 7.1.1).

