1. Study visits, beginning with Visit 3, should be planned for the study day specified in the protocol. If it is not possible to complete the visit on the planned day, or if an emergency occurs, the protocol does allow for some exceptions as long as the minimum and maximum between injection and between treatment cycle restrictions are maintained. See Section 7.1.1 for details.
2. Sitting systolic and diastolic blood pressure, heart rate, and body temperature.
3. Including weight every six months (Weeks 78 and 104; Visits 17 and 22 in the treatment phase and all visits in the extended follow-up phase) and height at the end of the DBPC phase (Week 104/Visit 22/Early Termination) and last extended follow-up visit.
4. Hematology, biochemistry, urinalysis. See [Appendix B](#) for complete list. Coagulation tests will be performed locally at the screening assessment only.
5. Blood samples for PK will be taken 2 hours after the last dose of each cycle.
6. Fasting samples for biomarker analysis.
7. PGt samples will be collected for consenting subjects only.
8. Urine pregnancy test at scheduled time points (prior to IMP injection) and prior to each X-ray and MRI.
9. X-rays of both the target and the contralateral knee will be taken during screening, at Week 104/Visit 22, and at the last EF visits; X-rays of only the target knee will be taken at other time points. During screening, a long-axis view of the target knee will be taken in addition to the anterior/posterior view.
10. At time points where IMP administration is scheduled, X-rays and MRIs may be performed up to 3 days before the planned day of IMP administration. At time points where there is no IMP administration scheduled, X-rays and MRIs may be performed within ± 4 days (DBPC treatment phase) or ± 7 days (extended follow-up phase) of the planned day.
11. At visits where IMP is injected, synovial fluid will be collected as part of the i.a. injection procedure, using the same needle that will be used for IMP injection. PK will be analyzed in synovial fluid at all indicated sampling time points. If the volume of synovial fluid collected permits, biomarkers will also be analyzed at Week 52/Visit 12.

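### Protocol Appendix E, Table 6 leaves out the pregnancy-test mark at four injection visits (V13, V14, V18, V19) where the protocol text requires a pre-dose test

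*Protocol*

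**What the plan says.** Three places in the protocol body give the same rule for women of childbearing potential.

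- Section 7.1.3: "urine pregnancy tests will be performed before dosing on each treatment day".
- Section 7.1.3.2: "Urine pregnancy testing will be conducted in women of childbearing potential prior to each injection".
- Section 7.4.3: "For women of childbearing potential, pregnancy tests will be performed at the time points shown in" Appendix E, which it describes as "during screening, before each injection of IMP, and at each visit involving X-ray and MRI".

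Section 7.1.3.2 also names the injection visits in the second treatment year: "Cycle 3: Weeks 52, 53, and 54 (Visits 12, 13, and 14" and "Cycle 4: Weeks 78, 79, and 80 (Visits 17, 18, and 19".

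Appendix E, Table 6 covers V12 to V28. Its pregnancy-test row, beginning "Pregnancy test (urine", is marked at V12, V17, V22, V24, V26 and V28. Footnote 8 to that row reads: "Urine pregnancy test at scheduled time points (prior to IMP injection) and prior to each X-ray and MRI".

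**The concern.** Section 7.4.3 says both that Appendix E shows the test times and that those times include every injection. For Table 6 both statements cannot be true, because four of its six injection visits carry no test mark.

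The schedule is a working document. Section 7.1 directs sites to Appendix E for what to do at each visit, and Section 7.4.2 requires trial medication to stop immediately if a subject becomes pregnant. A site working from the marks alone could give the second and third injections of cycles 3 and 4 without the required pre-dose test.

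The body text also offers a path to the same shortened list. Section 7.1.3 supports its rule with a cross-reference to Section 7.1.3.3, which covers only the major efficacy visits. Within Table 6 those are V12, V17 and V22, exactly the treatment-phase visits that are marked.

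**Working it through.** No statistical figure is involved. The check compares the marked cells with the rule in the text.

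**Table 6, row by row**

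| Row | Visits marked |
|---|---|
| Injection | V12, V13, V14, V17, V18, V19 |
| Target knee MRI | V12, V17, V22, V24, V26, V28 |
| Knee X-ray | V12, V22, V24, V26, V28 |
| Urine pregnancy test | V12, V17, V22, V24, V26, V28 |

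The injection row agrees with the cycle 3 and 4 visits named in Section 7.1.3.2.

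**Marks required.** Under Section 7.4.3 the test is due at any visit with an injection or with imaging.

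- Injection visits: 6.
- Imaging visits (MRI or X-ray): 6.
- Visits in both sets: V12 and V17, so 2.
- Required: 6 + 6 − 2 = 10.
- Present: 6.
- Missing: 10 − 6 = 4, namely V13, V14, V18 and V19.

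The pregnancy-test row is identical to the MRI row. It meets the imaging part of the rule and misses every injection visit that has no imaging.

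**Comparison with Table 5.** Table 5 covers Visits 1 to 11. Its pregnancy-test row is marked at V1b, V2, V3, V4, V7, V8 and V9. Section 7.1.3.2 puts the cycle 2 injections at V7, V8 and V9, so all six injection visits of cycles 1 and 2 are marked. Over the whole trial, 4 of 12 injection visits are unmarked. Table 5 does not contradict Table 6, since the visits differ, but it shows the pattern Table 6 should follow.

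**Could this come from reading the table out of the PDF?** There are known faults. The Table 6 diary and vital-signs rows show 18 marks for 17 visits, and the Table 5 injection row reads one column early in cycle 2. A column shift moves marks but does not reduce ten to six. The four columns in question are also not blank elsewhere in Table 6:

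- V13 and V18: diaries, vital signs, synovial fluid and injection, 4 marks each.
- V14 and V19: those four plus PK serum, biomarker serum and biomarker urine, 7 marks each.
- Total: 4 + 7 + 4 + 7 = 22 marks.

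**Does footnote 8 restore the tests?** Not clearly. It ties the test to scheduled time points, and the marks are what schedule them. The parenthesis about injection can be read as timing within a marked visit, while the word *each* is attached only to X-ray and MRI. Table 5 footnote 12 has nearly the same wording, but its row is fully marked, so nothing there depends on the footnote.

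**Time since the last marked test.** Section 7.1.1 plans 7 days between injections within a cycle and allows 6 to 9.

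- V13 (after V12) and V18 (after V17): 7 days planned, 6 to 9 allowed.
- V14 and V19: 2 × 7 = 14 days planned, 2 × 6 = 12 to 2 × 9 = 18 allowed.

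**The case against.** The strongest reply is that this is an editorial slip. The rule is plain in three sections, one of which governs the injection visits, and Section 7.4.3 tells the reader how to interpret Appendix E in the sentence that cites it. A missed test needs a site to overlook all three. That is fair as to size, but it does not remove the mismatch: no text exempts the four visits, and sites are sent to the schedule for visit procedures.

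A second reply concerns timing. SAP Section 9 says the study was fully enrolled as of September 2014. Using the widest windows in protocol Section 7.1.1, each cycle spans at most 2 × 9 = 18 days and each gap at most 27 × 7 = 189 days. The last injection therefore falls at most 4 × 18 + 3 × 189 = 72 + 567 = 639 days after the first. Counted from 30 September 2014, that is about 30 June 2016, before the final SAP of 11 August 2016. Assuming first injections by the end of September 2014 and visits within window, no injections remained by then, and the remaining follow-up imaging visits are already marked. This stands: by that date the correction tidies the record, and it could have changed practice only earlier.

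Third, extraction that adds marks might also lose them. Table 5 shows no physical-examination mark at V11, although Section 7.1.3.4 requires one, and the text cannot show whether that mark was lost or never there. This lowers certainty slightly. Random loss of exactly the four marks that leave the row identical to the MRI row is unlikely.

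**Conclusion.** The inconsistency is real. Table 6 has 6 pregnancy-test marks where the protocol's own rule needs 10, and the four missing ones are all injection visits: V13, V14, V18 and V19.

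It is a low-priority correction. The test applies only to women of childbearing potential, who must use contraception with a failure rate below 1% per year under Section 5.3.1, and the last marked test is about 7 or 14 days earlier. The counts are table cells, not subjects; the documents do not give the number of women of childbearing potential, so no number at risk can be stated. Power, error rates, endpoints and analyses are unaffected.

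The conclusion assumes that the extracted pregnancy-test row reproduces the original marks, which its exact match with the MRI row supports.

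**What to change.** In Appendix E, Table 6, add a mark in the pregnancy-test row at V13, V14, V18 and V19. The row would then read V12, V13, V14, V17, V18, V19, V22, V24, V26 and V28.

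Reword footnote 8 to: *Urine pregnancy test prior to each IMP injection and prior to each X-ray and MRI.*

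Leave the requirement in Sections 7.1.3, 7.1.3.2 and 7.4.3 as it is. Optionally, point the cross-reference in Section 7.1.3 to Section 7.1.3.2, which states the rule for every injection.

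The cost is four table cells and one footnote. No testing is added, because the text already requires these tests.

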Appendix F: Pain in Other Joints

DoLD Day of Last Dose
ECG Electrocardiogram
ECM Extracellular matrix

ECS Enabling Clinical Sciences

eCRF Electronic Case Report Form

ESR Erythrocyte sedimentation rate

EudraCT European Union Drug Regulating Authorities Clinical Trials

Sprifermin (AS902330) Statistical Analysis Plan (Final) EMR700692 006 – v1.0

(European clinical trials database)

FGF Fibroblast growth factor

FGF-18 Fibroblast growth factor-18

FORWARD FGF-18 Osteoarthritis Randomized trial With Administration of

Repeated Doses

GCP Good Clinical Practice

GED Global Early Development

HLT High-Level Term

hsCRP High-sensitivity C-reactive protein

i.a. Intra-articular(ly)

ICF Informed Consent Form

ICH International Conference on Harmonization

ICOAP Measure of Intermittent and Constant Osteoarthritis Pain

IDMC Independent Data Monitoring Committee

IL1RN Interleukin 1 Receptor Antagonist
IMP Investigational Medicinal Product

IND Investigational New Drug

ITT Intention-to-Treat

ITT2 Second Intention-to-Treat

IVRS Interactive Voice Response System

JSW Joint space width

KL Kellgren-Lawrence

KOOS Knee Injury and Osteoarthritis Outcome Score

KOOS QOL Knee Injury and Osteoarthritis Outcome Score quality of life subscale

PPD

LLN Lower limit of normal (range)

LOCF Last Observation Carried Forward

Max Maximum

MCID Minimally clinically important difference

mcg Microgram(s)

MedDRA Medical Dictionary for Regulatory Activities

Min Minimum

Sprifermin (AS902330) Statistical Analysis Plan (Final) EMR700692 006-v1.0

mJSW Minimum joint space width mITT Modified Intention-to-Treat

MOP Manual of Operations

MOS SF-36 Medical Outcomes Study Short Form-36 General Health Survey

MRI Magnetic resonance imaging

m2ITT Second Modified ITT
NRS Numerical Rating Scale

NSAIDs Nonsteroidal anti-inflammatory drugs

OA Osteoarthritis

OAI Osteoarthritis Initiative

OARSI Osteoarthritis Research Society International

OMERACT-OARSI Outcome Measures in Rheumatology – Osteoarthritis Research Society

International (responder criteria)

PD Pharmacodynamic(s)

PGA Patient's Global Assessment

PGIC Patient Global Impression of Change

PGX Pharmacogenomics
PK Pharmacokinetic(s)
POC Proof of concept

PP Per Protocol

PRO Patient Reported Outcome

PT Preferred Term
Q1 First quartile
Q3 Third quartile
QOL Quality of life

QPD Quantitative Pharmacology and Drug Disposition

QTc Corrected electrocardiogram QT interval

rhFGF-18 Recombinant human fibroblast growth factor 18

SAE Serious Adverse Event SAP Statistical analysis plan

SD Standard deviation

SDTM Study Data Tabulation Model

Sprifermin (AS902330) Statistical Analysis Plan (Final) EMR700692 $_006-v1.0$

SNP Single nucleotide polymorphism

SOC System Organ Class

SOP Standard Operating Procedures

TEAE Treatment Emergent Adverse Event

TLFs Tables, Listings and Figures

ULN Upper limit of normal (range)

VAS Visual analogue scale

W Week

WBC White blood cell

WOMAC Western Ontario and McMaster Universities Osteoarthritis Index

WORMS Whole Organ Magnetic Resonance Imaging Score

4 Modification History

Unique Identifier for SAP Version	Date of SAP Version	Author	Changes from the Previous Version
0.1	28Jun2013	PPD	First version
0.2	08Apr2014		Second version
0.3	21 Jul2014		Third version
0.4	18 Aug 2014		Fourth version
0.5	24 Sep 2014		Fifth draft
0.6	14 Oct 2014		Minor changes
0.7	13 July 2015		Changes include inclusion of biochemical markers and alignment with the imaging charter (interand intra-reader reliability testing)
0.8	3 August 2015		Implement comments from PPD and PPD
0.9	01Oct2015		Minor changes
0.10	15Oct2015		Minor changes
0.11	04Jan2016		Minor Changes, ready for finalization
0.12	21Apr2016		Major Changes, ready for finalization
0.13	14Jun2016		Minor Changes, ready for final review
0.14	10Aug2016		Minor changes, ready for final check before signing
1.0	11Aug2016		Final version

5 Purpose of the Statistical Analysis Plan

The purpose of this Statistical Analysis Plan (SAP) is to document technical and detailed specifications for the final analysis of data collected for protocol EMR700692_006. Results of the analyses described in this SAP will be included in the Clinical Trial Report (CTR). Additionally, the planned analyses specified in this SAP will be included in regulatory submissions or future

manuscripts. Any additional analyses performed to provide results for inclusion in the CTR, but not specified in this SAP, will be clearly identified in the CTR.

The statistical analysis will be performed by Analysis of pharmacokinetic data, antibody data, biomarkers as well as modeling and simulation will be performed by Merck-Serono. Details on the analysis of pharmacokinetic data (including antibody data), and exploratory biomarkers are specified in Sections 16.3 and 16.4, respectively. Analysis of antibodies to sprifermin is part of the safety evaluation and is specified in Section 16.3 and Section 17. The biomarkers statistical analysis plan (BSAP) and the Modeling and Simulation plan will be detailed by Merck-Serono in separate SAP documents. However, selected biomarker analyses (e.g., pharmacogenomics [PGX] and other biochemical markers), as presented in this SAP, will be performed by PPD . List of key Tables, Figures and Listings are included in Appendix 19.5.

6 Summary of Clinical Trial Features

Trial Objectives

In subjects with primary osteoarthritis of the knee treated with different intra-articular (i.a.) dosages of Sprifermin:

Primary

To evaluate structural changes in cartilage thickness in the total femorotibial joint of the target knee in terms of imaging by magnetic resonance imaging (MRI)

Secondary

- To evaluate different dose regimens of sprifermin
- To evaluate changes in symptoms of osteoarthritis (OA)
- To evaluate changes in structure in terms of imaging by X-ray
- To evaluate other changes in cartilage morphology in terms of imaging by MRI (sub-regions)
- To evaluate changes in physical functioning
- To evaluate the safety of sprifermin
- To evaluate the pharmacokinetics (PK) of sprifermin in serum and in synovial fluid following i.a. injection

Exploratory

- To evaluate responder criteria in symptoms
- To explore treatment effect on OA pain and other patient-reported outcomes (PROs)

- To evaluate changes in quality of life (QOL)
- To explore treatment effect on the knee joint and bone structures by MRI
- To evaluate long-term treatment effects
- To explore the relationship between the change over time in synovial, serum, and urine biomarkers (e.g., cartilage and bone tissue turnover markers, inflammation markers) and the response to the drug
- To evaluate potential associations of biomarkers (e.g., genetic variations or protein biomarkers measured at baseline) with drug response, and/or disease severity or disease progression
- To explore the relationship between dosing (dose and regimen), cartilage structure, and clinical scores as a function of time, by means of modelling

Trial Endpoints

Primary

Change from baseline in cartilage thickness in the total femorotibial joint as evaluated by MRI at 2 years

Secondary

- Changes from baseline in the Western Ontario and McMaster Universities Osteoarthritis Index (WOMAC) total score and in the WOMAC pain, function, and stiffness index scores over 2 years
- Change from baseline in the 20-meter walk test over 2 years
- Change from baseline in the Patient's Global Assessment (PGA) over 2 years
- Change from baseline in minimal Joint Space Width (JSW) in the medial and lateral compartments as evaluated by X-ray over 2 years
- Change from baseline in cartilage thickness in the medial and lateral compartments over 2 years
- Change from baseline in cartilage volume in the medial and lateral compartments over 2 years
- Synovial fluid levels of sprifermin/FGF-18
- Serum levels of sprifermin/FGF-18

Safety endpoints

- Nature, incidence and severity of local and systemic Adverse Events (AEs).
- Incidence of acute inflammatory reactions (AIRs), defined as increase of pain by 30 mm on a 100 mm visual analogue scale (VAS) and a self-

- reported synovial fluid effusion (i.e., joint swelling) within 3 days following i.a. injection (see Section 7.4.1.1 of the protocol)
- Changes in laboratory safety parameters, vital signs, 12-lead electrocardiogram (ECG) parameters, weight, and physical examinations
- Occurrence of binding and neutralizing antibodies to sprifermin/FGF-18

Exploratory

- Outcome Measures in Rheumatology Osteoarthritis Research Society International (OMERACT-OARSI) responder rate at 2 years
- Patient Global Impression of Change (PGIC) over 2 years
- Changes from baseline in the scores of the Knee Injury and Osteoarthritis
 Outcome Score quality of life subscale (KOOS QOL) and the SF-36
 Medical Outcomes Study Short Form-36 General Health Survey (MOS
 SF-36 questionnaire) over 2 years
- Change from baseline in Knee Injury and Osteoarthritis Outcome Score (KOOS) Symptom Index over 2 years
- Change from baseline in Numerical Rating Scale (NRS) pain score in the target and contralateral knee over 2 years using an 11-point NRS
- Change from baseline in presence of pain in other joints over 2 years
- Change from baseline in Measure of Intermittent and Constant Osteoarthritis Pain (ICOAP) scores over 2 years
- Change over time in structural features of the knee joint (e.g., synovium, menisci, bone, and other structures) as evaluated by MRI
- Change from baseline in serum, urine, and synovial markers associated with administration of the compound
- Baseline biochemical biomarkers and/or genetic markers associated with response to treatment or disease progression (response assessed by MRI, X-ray and/or questionnaire)
- Changes in MRI outcomes, WOMAC scores, 20-meter walk test, PGA, PGIC, JSW, OMERACT-OARSI responder rate, KOOS QOL, KOOS Symptom Index, MOS SF-36, NRS pain score in the target and contralateral knee, presence of pain in other joints, ICOAP, safety laboratory values, and vital signs over the extended follow-up period and nature, incidence and severity of local and systemic AEs during the extended follow-up period (to be summarized descriptively)
- Relationship between dosing (dose and regimen), cartilage structures, and clinical scores as a function of time

Trial Design	This is a multicenter, randomized, double-blind, placebo-controlled, parallel-group Phase II trial of sprifermin administered i.a. in subjects with primary OA of the knee and Kellgren-Lawrence (KL) grade 2 or 3.
	The trial consists of a screening period lasting up to 42 days, a 2-year (104-week) double-blind placebo-controlled (DBPC) treatment phase, which will start at randomization (Week 0/Visit 2) and a 3-year extended follow-up phase. Please see table 5 and 6 (Appendix E) in the clinical trial protocol. Please see below for specification of dose groups (Trial Product).
Number of Subjects	The trial will randomize approximately 545 subjects (109 per treatment group).
Trial Product	Sprifermin (also known as: recombinant human fibroblast growth factor 18 [rhFGF-18]; AS902330) 30 mcg or 100 mcg, administered intra-articularly (i.a.).
	Subjects will receive 4 cycles of treatment (each consisting of 3 once-weekly i.a. injections over 3 consecutive weeks) at intervals of 6 months.
	Subjects will be randomized in equal allocation to one of 5 treatment groups:
	• 4 cycles of sprifermin (100 mcg per injection, total dose 1200 mcg)
	• 2 cycles of sprifermin (100 mcg per injection) alternating with 2 cycles of placebo (total dose 600 mcg)
	• 4 cycles of sprifermin (30 mcg per injection, total dose 360 mcg)
	• 2 cycles of sprifermin (30 mcg per injection) alternating with 2 cycles of placebo (total dose 180 mcg)
	• 4 cycles of placebo (total dose 0 mcg)
Treatment and Trial Duration	Planned treatment duration is 2 years.
	Follow-up duration is 3 years.
Trial Periods (if applicable)	The screening period will comprise a period of 4 to 42 days during which a subject's eligibility will be determined, beginning at signature of the Informed Consent Form (ICF).
	During the screening visits, eligibility will be assessed and the target knee will be defined. At the baseline visit, eligibility will be confirmed, randomization will occur, and the first IMP injection will be given (Week 0/Visit 2). The last of the four cycles of 3 injections of IMP will begin on Week 78/Visit 17, and the last dose of IMP is scheduled to be administered at Week 80/Visit 19.

Trial visits during the two-year DBPC treatment phase will take place at Weeks 0 (randomization and first IMP injection), 1, 2, 3, 12, 26, 27, 28, 29, 38, 52, 53, 54, 55, 64, 78, 79, 80, 81, 90, and 104.

Major efficacy assessments will take place on the first day of each treatment cycle and then at the end of the DBPC treatment phase (Week 104/Visit 22).

Minor efficacy assessments will take place 9 weeks after each treatment cycle.

Adverse Events (AE) and concomitant medications will be reviewed and vital signs will be measured at all trial visits.

Trial assessments during the 3-year extended follow-up phase will take place at 6-month intervals from Week 104/Visit 22 through Week 260/Visit 28.

Randomization and Blinding

Eligible subjects will be randomized to one of the 5 treatment parallel groups with an allocation ratio of 1:1:1:1:1. Randomization will be stratified by country.

The central randomization service's IVRS will be used to randomize subjects to treatment.

The allocated randomization number will only be used for dosing.

The IVRS will also be used to assign a blinded treatment kit at each subsequent treatment visit.

7 Sample Size/Randomization

As described in protocol Section 8.1: The sample size was determined for the primary endpoint: Change from baseline in cartilage thickness in the total femorotibial joint as evaluated by quantitative MRI at 2 years.

[figure not shown]
This trial is set up to detect a potential dose relationship, based on the total dose of sprifermin received over the 2 years, in limiting the reduction of or increasing the cartilage thickness in the total femorotibial joint, assuming:

- 1. A mean change from baseline at 2 years:
 - -0.03 mm in the placebo group (i.e., 0 mcg over 2 years)
 - -0.01 mm in the sprifermin 30 mcg once a year group (i.e., 180 mcg over 2 years)
 - +0.01 mm in the sprifermin 30 mcg twice a year group (i.e., 360 mcg over 2 years)
 - +0.01 mm in the sprifermin 100 mcg once a year group (i.e., 600 mcg over 2 years)
 - +0.03 mm in the sprifermin 100 mcg twice a year group (i.e., 1200 mcg over 2 years)
- 2. A common SD (standard deviation) of 0.10 mm
- 3. A type-one error, α , of the primary efficacy analysis set at 5% two-sided
- 4. Normal distribution.

The above assumptions were based on available MRI data from the Osteoarthritis Initiative (OAI) (http://oai.epiucsf.org/datarelease/) and from the Phase I Proof of concept (POC) trial (28980).

Figure 1 Expected Mean Changes in Cartilage Thickness (mm) in Total Knee at 2 Years, SD=0.10

SD: standard deviation

A minor deviation from linearity has been introduced in these hypotheses based on the expectation of similar changes for the sprifermin 30 mcg twice a year, and sprifermin 100 mcg once a year groups. Indeed, according to the current knowledge of the biological mechanism of action of sprifermin, the treatment effect of the highest dose (100 mcg) given once a year could be similar to that of a lower dose (30 mcg) given twice a year. Moreover, the variability of the measure is large, and therefore a deviation from perfect linearity may be expected.

Calculations showed that:

- 55 evaluable subjects in each group (total 275 subjects) will ensure a power of 90% for detecting a linear dose relationship using a linear trend test,
- 76 evaluable subjects in each group (total 380 subjects) will ensure a power of 90% for detecting an overall treatment effect (meaning that at least one group differs from the other groups) as well.

Based on recent literature and other trial experience (see protocol references 45 and 46), the subject discontinuation rate is estimated to be close to 30% at two years. Assuming a 30% drop-out rate, a total of 545 subjects should be randomized (109 subjects per group) in order to detect an overall treatment effect.

In order to be able to demonstrate that structural improvement translates into symptomatic benefit, it is important that the study be adequately powered to detect significant differences in normalized WOMAC scores. With 76 evaluable subjects per treatment group, the power to show a statistically

significant difference between at least one active treatment group and the placebo group for the secondary WOMAC endpoints ranges from 69% to 87% for the total score, from 80% to 99% for the pain score and from 53% to 83% for the function score, depending on the expected mean difference from placebo (see Table 1).

Table 1 Power Calculations for Pairwise Differences (Sprifermin versus Placebo) on Normalized WOMAC Scores with 76 Evaluable Subjects per Treatment Group

	Expected mean difference from Placebo	Common SD	Power
Total Coons Name discal	8 points	20	69%
Total Score - Normalized (range 0-100 points)	9 points		79%
(range o- roo points)	10 points		87%
Pain Score - Normalized	10 points	22	80%
(range 0-100 points)	15 points		99%
Function Score -	7 points	21	53%
Normalized	9 points		75%
(range 0-100 points)	10 points		83%

SD: standard deviation; WOMAC: Western Ontario and McMaster Universities Osteoarthritis Index

For reference, the minimally clinically important difference (MCID) in WOMAC scores is considered to be about 10% of the maximum score, which correspond to approximately 10 points for the total WOMAC score, 7 points for the WOMAC function index (activities of daily living) score, 2 points for WOMAC pain index score, and 1 point for the WOMAC stiffness index score) [1]. WOMAC scores that are considered MCID are highlighted in bold type in the table above.

Please note that the power calculations did not include adjustment for multiplicity. Randomization is described in Section 6 of the protocol.

8 Overview of Planned Analyses

[figure not shown]
The protocol specifies a two-year treatment phase (Baseline to Year 2) followed by a three-year extension phase (Years 2 to 5). Subjects and sites will remain blind to treatment throughout the entire protocol (Baseline to Year 5). The statistical analysis will be performed in three steps (see "Study Design" figure below):

Reporting of the DBPC treatment phase: After the last subject's last visit of the DBPC treatment
phase, the data collected until the end of the DBPC treatment phase will be cleaned and released,
a Blind Data Review Meeting will be held to clarify potential remaining issues before the
database can be partially locked (this terminology is used here to differentiate data coming from
the DBPC treatment phase vs. extended follow-up phase, but all processes for formal database
lock will be followed); if all participants of the Blind Data Review Meeting are in agreement

